### **6.4.2.4. Health Economics Assessments**

The following health economics endpoints will be summarized by treatment group for the micro-ITT Population:

- Duration of antibiotic utilization;
- Duration of stay in the ICU; and
- Duration of hospitalization.

Duration of antibiotic utilization is defined as the number of days that the subjects received antibiotic therapy after the administration of the study drug.

Duration of stay in the ICU is defined as the total number of days of ICU stay after the administration of the study drug.

Duration of hospitalization is defined as the total number of days of hospitalization after the administration of the study drug.

Duration of antibiotic utilization, duration of stay in the ICU, and duration of hospitalization will be analyzed using an ANOVA model, with treatment as a main effect, site and baseline

randomization strata as factors. The treatment differences in LS means, corresponding standard errors, 95% confidence intervals, and p-values will be obtained from the ANOVA model and presented.

### 6.4.3. Microbiological Endpoints

Microbiological endpoints include the following:

- Eradication of index *P. aeruginosa* at Day 21 and 28;
- Re-infection/new infection defined as a reoccurrence of pneumonia due to *P. aeruginosa* within the 28-day follow-up period; and
- Change in bacterial load related to the index *P. aeruginosa* on the basis of quantitative or semi-quantitative cultures by the local microbiological laboratory.

Microbiological endpoints of eradication and re-infection/new infection will be determined based on quantitative/semi quantitative cultures performed by the local laboratory and testing of isolates performed by a central microbiology laboratory.

For microbiological outcome of eradication of index *P. aeruginosa*, if no specimen of respiratory secretions is obtained at the specific time point, the nearest microbiological data available prior to that day (Day 7, 14, 21, or 28) will be used, i.e. using LOCF approach. When there is no specimen obtained prior to that day, microbiological outcome will be assessed as “Eradicated” only if the study subject is not receiving any antibiotic active against the initial strain after the study drug administration and prior to that day and displays no signs and symptoms of pneumonia.

The eradication rate of index *P. aeruginosa* and reinfection rate of pneumonia due to *P. aeruginosa* will be summarized by treatment group based on the micro-ITT Population and analyzed using a stratified CMH test based on the stratification factors at randomization. The P-value from the stratified CMH test will be presented.

Change in bacterial load ( $\log_{10}\text{cfu/mL}$ ) related to the index *P. aeruginosa* based on the local microbiological laboratory will be presented by treatment group for the micro-ITT Population.

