Study subjects will receive a single treatment dose (at Day 0) in addition to SOC antibiotic treatment, and then enter a safety, efficacy and PK follow-up study period for a total study duration of 28 days. The selection of SOC antibiotics is made in accordance with local best practices at the discretion of the investigator and should not exceed a duration of 14 days.

The clinical course of pneumonia will be assessed daily by the investigator. Once Clinical Cure has been determined, the clinical status of the subject will be monitored to confirm continuation of Clinical Cure, re-infection (pneumonia due to *P. aeruginosa*), or new infection (pneumonia due to an unknown pathogen or a pathogen other than *P. aeruginosa*). “Clinical Cure” can be declared at any time during the study by the PI provided, that the required criteria are met either based on documented improvements in signs and symptoms, +/- changes documented by chest X-ray (if performed as part of SOC), as interpreted by the investigator.

The assessment of Clinical Cure (resolution of pneumonia) by the site investigator will be used for the primary analysis. An adjudication committee will apply newly defined Clinical Cure criteria post hoc in a secondary analysis. “Clinical Cure” will be assessed for analytical purposes on Day 7, 14, 21 (primary efficacy endpoint) and 28.

Clinical safety assessments will be performed on an ongoing basis while predefined laboratory assessments will be performed at baseline, and thereafter at Day 4, 7, 14, 21, and 28. Test results obtained for medical reasons between these mandatory time points will be assessed for adverse events and documented accordingly.

Secondary efficacy endpoints will be assessed in a similar manner during the 28-day period, when appropriate, daily when possible (e.g., time on mechanical ventilation including if tracheostomy is in place, time on supplemental oxygenation, measures of respiratory health such as changes in PaO2/FiO2 using arterial blood gases and/or pulse oximetry measurements), or upon occurrence (e.g., antibiotic utilization, duration of stay in the ICU, duration of hospitalization, duration of intubation with ventilation, or duration of mechanical ventilation if tracheostomy in place).

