
 
1. To be performed if medically necessary. Follow-up airway specimens to be obtained as medically necessary and prior to extubation and at Day 28 (if not extubated prior to then) for quantitative or semi-quantitative culture.
 
2. SOFA and respiratory data to be collected on Day 0, 12 hours after treatment initiation and on Day 4, 7, 14, 21, 28 while intubated and mechanically ventilated. Parameters for SOFA score calculation should not be older than 72 hours.
 
3. ADA only at screening / baseline and Day 28, or at early termination.
 
4. Pre-dose PK sample to be obtained prior to treatment initiation.
 
5. PK samples to be obtained for the FULL PK sub-study at the following times after initiation of treatment: 2 hours (end of infusion), 4h, 12h, and 24 hours and 1 sample at each of the following visits: Day 4, 7, 14, 21, and 28.
 
6. PK samples for the SPARSE PK sub-study at the following times after initiation of treatment: 1 sample at 2 hours (end of infusion), 1 sample at either 4h, 12h, or 24 hours post-treatment initiation (inclusive) and 1 sample at any of the following visits: Day 4, 7, 14, 21, or 28.
 
7. Eligible subjects are randomized on Day -1, Treatment day is Day 0 for the purpose of monitoring and collecting the required samples over the first 24 hours.
 
8. Clinical Cure will be assessed at Day 7, 14, 21, 28 for the analytical purposes.
 
9. Discharge data to be obtained when discharge occurs or Day 28, whichever occurs first.
 
10. Patients with pneumonia who are intubated are eligible for screening regardless of the type of pneumonia, which will be recorded at the time of screening for all study subjects.
 
11. Vital signs will be recorded at baseline prior to treatment (time 0) and then at 1, 2, 4, 12, and 24 hours post treatment. Vital signs will also be recorded daily thereafter.
 
12. In addition to the screening timepoint, chest x-ray(s) are to be taken at any time as medically indicated.
 
13. Women of child bearing potential must take a urine or serum pregnancy test at the time of Screening.
 
14. For subjects with early discharge, effort must be made to perform all protocol defined procedures outlined for End of Study/Early Termination.
 
15. Subjects who decide to discontinue study assessments prior to Day 28 will receive a study exit safety follow-up phone call on key days (Day 4, 7, 14, 21, 28) until Day 28 (+7 days) to assess Clinical Cure, survival and the status of any adverse events.
 
16. Changes in PaO2/FiO2 ratio (e.g. by arterial blood gases), if available and whenever possible OR changes in non-invasive measures of oxygenation (e.g. by pulse oximetry)
 
17. A few days before or after the specified date is acceptable (<math>\pm 2</math> days)
 
					

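### The re-infection/new infection endpoint is defined as *P. aeruginosa* recurrence only, contrary to the design text, so no by-arm rate of new infection or of any recurrent pneumonia is planned

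*SAP*

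**What the plan says.** The design text in SAP 3.1 says that, after Clinical Cure, subjects are monitored for continued cure, for re-infection (pneumonia due to *P. aeruginosa*), "or new infection (pneumonia due to an unknown pathogen or a pathogen other than" *P. aeruginosa*). Protocol 3.1 and the Protocol synopsis define the terms in the same way.

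The objectives (Protocol synopsis, Protocol 2.5, SAP 2.6) and the analysis text in SAP 6.4.3 join the two terms and give them one definition: "Re-infection/new infection defined as a reoccurrence of pneumonia due to" *P. aeruginosa* within the 28-day follow-up. SAP 6.4.3 classifies the endpoint from local cultures and central testing of isolates. It then names one quantity for the stratified CMH test in the micro-ITT population, besides eradication: the "reinfection rate of pneumonia due to" *P. aeruginosa*.

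The numbered endpoint lists in SAP 5.3 and Protocol 7.3 contain neither re-infection nor new infection.

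On specimens, footnote 1 to SAP Table 1 reads: "Follow-up airway specimens to be obtained as medically necessary and prior to extubation and at Day 28", the last only if the subject has not been extubated earlier. The missing-specimen rule in SAP 6.4.3 is written for eradication and does not extend to recurrence.

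**The concern.** The same term carries two incompatible meanings. In the design text, new infection is by definition not known to be *P. aeruginosa*. In the objective and the analysis it is by definition *P. aeruginosa*. A result reported under the joint label would contain no new infections in the design sense.

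This matters because Protocol 5.2 describes the antibody's target as specific to *P. aeruginosa*, and subjects with several pathogens may be enrolled. One reasonable question for a single-species agent is whether fewer *P. aeruginosa* recurrences mean fewer recurrent pneumonias, or only a change in the organism. A numerator limited to *P. aeruginosa* cannot answer that, and no other planned table gives the recurrence rate by pathogen or for any pathogen. The third hypothesis (Protocol 1.4, SAP 6.1.3) speaks of improved microbiological outcomes overall, which a one-species rate addresses only in part.

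**Working it through.** No stated figure belongs to this endpoint: neither document gives an expected recurrence rate or a power statement for it. The check is a comparison of texts, followed by an illustration of scale.

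**Step 1: classify each type of recurrence under both texts.**

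| Recurrent pneumonia within 28 days | SAP 3.1 / Protocol 3.1 | SAP 6.4.3 |
|---|---|---|
| *P. aeruginosa* grown | Re-infection | Event |
| Another pathogen grown | New infection | Definition not met: non-event |
| Pathogen unknown, including no usable culture | New infection | Definition not met: non-event; no explicit rule |

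The last two rows are the whole of new infection in the design text, and neither enters the numerator in SAP 6.4.3. The subjects remain in the micro-ITT denominator.

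**Step 2: look for the missing rate elsewhere.**
- SAP 5.3 and Protocol 7.3 do not list the endpoint.
- Time to Clinical Cure (SAP 6.4.2.1) runs to the first cure, so a later recurrence does not change it.
- Clinical Cure at Day 21 and Day 28 can be affected by a recurrence from any pathogen. It does not separate recurrence from failure to cure, or one pathogen from another.
- Adverse event tables (SAP 6.6.1) are by system organ class and preferred term. They are not built on the study's recurrence definitions.

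None of these gives a new-infection rate or an any-recurrence rate by arm.

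**Step 3: scale, on assumed inputs.** Let n = 77 per arm (the planned number, SAP 4), r = any-pathogen recurrence, and s = share of recurrences due to *P. aeruginosa*. Both r and s are assumptions. Uncounted recurrences per arm = n × r × (1 − s).

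| r | s = 0.3 | s = 0.5 | s = 0.7 |
|---|---|---|---|
| 10% | 5.4 | 3.9 | 2.3 |
| 20% | 10.8 | 7.7 | 4.6 |
| 30% | 16.2 | 11.5 | 6.9 |

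The range is about 2 to 16 per arm.

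**Step 4: how replacement could look, and how little one result would prove.** Assume *P. aeruginosa* recurrence of 10% on placebo and 5% on Aerucin, and other or unknown pathogens in 5% and 10%. Any recurrence is 10% + 5% = 15% on placebo and 5% + 10% = 15% on Aerucin. The planned rate would be halved, with no difference in total recurrence. In counts, 77 × 0.10 = 7.7 and 77 × 0.05 = 3.85, so about 8 versus 4 subjects. Fisher's exact test (two-sided) gives p = 0.37. The unstratified pooled z-test gives z = (8/77 − 4/77) / √(0.0779 × 0.9221 × 2/77) = 1.20, p = 0.23. Power at the assumed 10% versus 5% is about 22%. The example shows what the definition can hide; it does not predict a result.

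**The case against.** Several points on the other side stand.

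- **The tested rate is correctly named.** SAP 6.4.3 calls it reinfection due to *P. aeruginosa*, which is what SAP 3.1 means by re-infection, and it follows the stated objective. A pathogen-specific endpoint is coherent for this product and should stay. The conflict lies in the joint term and its definition.
- **Other-pathogen pneumonia is not invisible.** A reader might infer that such events are lost to the trial. They are not. The subjects stay in the denominator, and status after cure is monitored for both kinds of event. Criterion 4 of SAP Table 2 refers to bacterial pneumonia in general. The adverse event exemption in Protocol 8.3 covers only worsening of the index infection.
- **Recurrences without a culture may be few.** A suspected recurrence is a plausible reason for a medically indicated specimen, and Protocol 6.5 accepts sputum after extubation. Protocol 9.5 gives microbiological outcome to an adjudication committee. The documents do not show how often a culture would be missing; telephone follow-up of discharged subjects (Protocol 8.8) makes it possible. This bears only on the unknown category. Recurrences with a known other pathogen remain uncounted.
- **A reader might infer that the plan would report a false benefit.** The documents do not support that. They give no recurrence rates, and even the assumed halving is far from significance at this sample size.
- **The stakes are limited.** The endpoint is absent from the hierarchical list in SAP 6.4.2 and carries no confirmatory claim.

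**Conclusion.** The inconsistency is in the current text of both documents and should be resolved before unblinding. The objective and analysis text define the joint term as *P. aeruginosa* recurrence; the design text defines new infection as the complement of that. As written, new infections are non-events for the endpoint that bears their name, and no by-arm rate of new infection or of any recurrent pneumonia is planned.

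The conclusion about definitions rests on the wording alone. Its numerical effect cannot be established from the documents: the figure of about 2 to 16 uncounted recurrences per arm depends entirely on the assumed recurrence rate and *P. aeruginosa* share. The primary analysis and the hierarchical secondary tests are unaffected. This is a worthwhile correction to a supportive endpoint, and no evidence that the trial's main conclusion would be wrong.

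**What to change.** 1. In SAP 2.6 and 6.4.3, Protocol 2.5 and the matching synopsis objective, replace the joint definition with the two definitions in SAP 3.1.
2. Add the endpoint to SAP 5.3 and Protocol 7.3, which omit it.
3. Keep the planned *P. aeruginosa* reinfection analysis. Report also, by arm in the micro-ITT population: new infection with another pathogen; recurrence with unknown pathogen, including recurrences with no usable culture; and any recurrent pneumonia.
4. Give the difference between arms with a 95% confidence interval for *P. aeruginosa* reinfection and for any recurrence. The other two categories can be descriptive.
5. State how a recurrence without a culture is classified, and by whom.

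The cost is SAP and protocol wording and a few table rows. Protocol 6.5 and 6.6 already require sites to document re-infection/new infection and to record any organisms identified. They name the two as one item, however, and the eCRF is not among the documents, so someone must check that the categories can be separated. The fuller table may also give a less favourable overall picture than the *P. aeruginosa* rate alone.

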2.5 Microbiological Efficacy Objectives

To assess the effect of Aerucin®, administered as a single dose as adjunct therapy in addition to standard antibiotic therapy for *P. aeruginosa* pneumonia, as compared to standard antibiotic therapy alone, on the following parameters:

1. Eradication of index *P. aeruginosa* at Day 21 and 28 post-treatment,
2. Re-infection/new infection defined as a reoccurrence of pneumonia due to *P. aeruginosa* within the 28-day follow-up period,
3. Reduction in bacterial load related to the index *P. aeruginosa*.

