Study subjects will receive a single treatment dose (at Day 0) in addition to SOC antibiotic treatment, and then enter a safety, efficacy and PK follow-up study period for a total study duration of 28 days. The selection of SOC antibiotics is made in accordance with local best practices at the discretion of the investigator and should not exceed the duration of 14 days.

The clinical course of pneumonia will be assessed daily by the investigator. Once Clinical Cure has been determined, the clinical status of the subject will be monitored to confirm continuation of Clinical Cure, re-infection (pneumonia due to *P. aeruginosa*), or new infection (pneumonia due to an unknown pathogen or a pathogen other than *P. aeruginosa*). "Clinical Cure" will be declared at any time during the study by the PI, provided that the required criteria are met either based on documented improvements in signs and symptoms, +/- changes documented by chest X-ray (if performed as part of SOC), as interpreted by the investigator.

The assessment of Clinical Cure (resolution of pneumonia) by the site investigator will be used for the primary analysis. An adjudication committee will apply newly defined Clinical Cure criteria post hoc in a secondary analysis. “Clinical Cure” will be assessed for analytical purposes on Day 7, 14, 21 (primary efficacy endpoint) and 28.

Clinical safety assessments will be performed on an ongoing basis while predefined laboratory assessments will be performed at baseline, and thereafter at Day 4, 7, 14, 21, and 28. Test results obtained for medical reasons between these mandatory time points will be assessed for adverse events and documented accordingly.

Secondary efficacy endpoints will be assessed in a similar manner during the 28-day period when appropriate, daily when possible, (e.g., Time on mechanical ventilation including if tracheostomy is in place; Time on supplemental oxygenation; measures of respiratory health such as changes in PaO₂/FiO₂ using arterial blood gases and/or pulse oximetry measurements), or upon occurrence (e.g., antibiotic utilization, duration of stay in the ICU, duration of hospitalization, duration of intubation with ventilation, or duration of mechanical ventilation if tracheostomy in place).

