6.6 Day 4, 7, 14, and 21: Required full assessments

- All daily assessments as detailed above are required whether the subject is in the ICU or has been transferred out of the ICU.
- Perform full assessment of the clinical status of pneumonia
- Document Clinical Cure, persistence or re-infection/new infection of index pneumonia using the daily assessments described above.
- Microbiology:
 - **Airway specimens are to be obtained:**
 - **At any time when as medically indicated**
 - **At the least, a valid airway specimen (BAL, mini-BAL or ETA) is to be obtained just prior to extubation. Ideally, an ETA specimen would be preferred for the airway culture. If BAL or mini-BAL, make sure that either BUN or urea is collected at or about the same time of sampling.**
 - **An aliquot (i.e. half of this specimen) is to be reserved for assessing bioavailability (refer to microbiology lab manual for instructions).**
 - **If not obtained on Day 4, 7, 14, and 21, the nearest specimen collected will be used to assess microbiological outcome.**
 - Obtain airway specimens for local and central laboratory assessment (by BAL, mini-BAL, or protected endotracheal tube aspiration) for standard microbial culture (quantitative, semi-quantitative). Other sampling methods, including sputum, are acceptable after extubation.
 - Obtain isolates for assessment by the central laboratory.
 - Record microbiological assessments from the local laboratory in the EDC system, including:
 - Assessment of the quality of the sample
 - Organism identification (genus and species)
 - Quantification
 - Any organisms identified,
 - The corresponding antibiotic susceptibility profile for each pathogen as determined by the local microbiology laboratory

- An assessment of microbiological outcome
- Physical exam
- Vital signs
- Adverse Events
- Concomitant Medications
- Respiratory health:
 - Mechanical ventilation parameters
 - PaO₂/FiO₂ ratio (e.g. by arterial blood gases), if available and whenever possible OR changes in non-invasive measures of oxygenation (e.g. by pulse oximetry)
 - Use of supplemental oxygen
- Laboratory tests.
 - Standard safety tests (required on these days regardless of medical need)

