#### **6.1.5. Handling of Dropouts and Missing Data**

Missing data will be handled as follows:

- For clinical outcome at Day 7, 14, 21, and 28, missing data will be handled using the nearest clinical data available prior to that day, i.e. last observation carried forward (LOCF) approach.
- For microbiological outcome at Day 7, 14, 21, and 28, missing data will be handled using the nearest microbiological data available prior to that day, i.e. **LOCF approach**.
- In cases of missing or incomplete dates [e.g. adverse event (AE) and concomitant medications], the missing component(s) will be assumed as the most conservative value possible. For example, AEs with missing start dates, but with stop dates either overlapping into the treatment period or missing, will be counted as treatment-emergent, taking the **worst-case approach**. When partial dates are present in the data, both a partial start date and/or a partial stop date will be evaluated to determine whether it can be conclusively established that the AE started prior to the start of study drug or ended prior to the start of study drug. If the above cannot be conclusively established based on the partial and/or present dates, then the AE will be considered as treatment-emergent. Actual data values will be presented in the data listings.
- A conservative approach will be taken to assess the relationship of an AE to study drug: if the relationship of an event is missing, it will be considered treatment-related. Missing severity for an AE will not be imputed.
- **Missing values for other variables will not be imputed** and only observed values will be used in data analyses and summaries.

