#### **6.2.3. Microbiological Intent-to-Treat Population (micro-ITT)**

The micro-ITT Population is defined as all ITT subjects for whom microbiological documentation of pneumonia due to *P. aeruginosa* at screening/baseline has been obtained.

The micro-ITT population will be used for efficacy analyses. Subjects will be analyzed by randomized treatment group.

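### SAP 6.4.3 tests re-infection over all micro-ITT subjects with no rule for death or non-resolution, which biases the comparison against a drug that raises cure

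*SAP*

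**What the plan says.** SAP 6.4.3 states that the "reinfection rate of pneumonia due to *P. aeruginosa* will be summarized by treatment group based on the micro-ITT Population" and is "analyzed using a stratified CMH test based on the stratification factors at randomization", with the p-value presented. The population is fixed by baseline microbiology: "all ITT subjects for whom microbiological documentation of pneumonia due to *P. aeruginosa* at screening/baseline has been obtained" (SAP 6.2.3). Neither cure nor survival enters that definition.

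The event is described in three places:

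- Protocol 2.5, repeated in SAP 2.6 and SAP 6.4.3: "Re-infection/new infection defined as a reoccurrence of pneumonia due to *P. aeruginosa* within the 28-day follow-up period".
- SAP 3.1, matching Protocol 3.1: "Once Clinical Cure has been determined, the clinical status of the subject will be monitored to confirm continuation of Clinical Cure, re-infection", followed by new infection.
- Protocol 6.6, with the same item in Protocol 6.5, tells sites to "Document Clinical Cure, persistence or re-infection/new infection of index pneumonia". Persistence is thus a status of its own.

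The only related data rule is in SAP 6.1.5, where for microbiological outcome "missing data will be handled using the nearest microbiological data available prior to that day". SAP 6.4.3 adds a fallback for eradication when no specimen exists. Neither rule covers death or non-resolution for re-infection.

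The labels also differ. Protocol 2.5, SAP 2.6 and SAP 6.4.3 put re-infection and new infection under one heading limited to *P. aeruginosa*. Protocol 3.1 and SAP 3.1 reserve new infection for an unknown organism or one other than *P. aeruginosa*.

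**The concern.** A subject must first resolve before pneumonia can reoccur. One whose pneumonia persists to Day 28 is recorded as persistence, and one who dies uncured has nothing to recur. Both remain in the micro-ITT denominator without an event, so two poor outcomes count on the favourable side. A subject who recurs and later dies is still an event.

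The number who can have the event grows with the cure rate, which is what the drug is meant to raise. Earlier cure also lengthens the time at risk within a fixed 28 days. The tested quantity is therefore the probability of resolving and then recurring. It can be higher on Aerucin when the drug has no effect on recurrence, and a reader could take that as a harm signal. Death is not a marginal event here: Protocol 1.1 cites pneumonia-attributed mortality of 20% to 33%.

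**Working it through.** **Inputs.** Day 21 cure of 65% on placebo and 85% on Aerucin, and 69 per group raised to 77 for 10% dropout (SAP 4, Protocol 9.2). SAP 3.1 describes the target of about 154 as microbiologically evaluable, so 77 per arm is used. The recurrence risk among resolved subjects, r, is not in the documents; it is assumed equal in both arms and varied.

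**1. The plan's own figures.** There is none for re-infection. The dropout step reproduces: 69/0.9 = 76.7, rounded up to 77. The stated power above 90% for cure does not (exact two-sided Fisher at 69 per group gives 73.3%). That is a separate matter and is not an input below.

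**2. Expected rates.** Micro-ITT rate = P(resolved) × r, with Day 21 cure standing in for P(resolved).
- r = 10%: 0.65 × 0.10 = 6.5% and 0.85 × 0.10 = 8.5%.
- Ratio at any r: 0.85/0.65 = 1.31 against Aerucin.

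**3. Effect on the test.** Exact enumeration of the unstratified Mantel-Haenszel chi-square, two-sided 0.05, 77 per arm, r = 10%:
- Expected events: 5.0 and 6.5.
- Chance that Aerucin's observed rate is the higher: 63%.
- Chance of a significant result against Aerucin: 6.0%, against a nominal 2.5%. In its favour: 0.7%.

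The chance of a significant result against Aerucin is 6.55% with 69 per arm, and 4.4% with 77 per arm and r = 5%.

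**4. Break-even.** Aerucin must cut recurrence among resolved subjects by 1 − 0.65/0.85 = 23.5% for the rates to be equal. A true 30% cut would show as 0.85 × 0.70/0.65 = 0.92.

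**5. Limit on r.** If recurrence before Day 21 cancels Day 21 cure, then ever resolved = Day 21 rate/(1 − r).
- r = 10%: 0.65/0.90 = 72.2% and 0.85/0.90 = 94.4%, which is possible; the ratio is still 1.31.
- r = 20%: 0.85/0.80 = 106%. r = 30%: 0.85/0.70 = 121%. Neither is possible.

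The ceiling on this reading is r = 1 − 0.85 = 15%. The larger cases (13.0% and 17.0% at r = 20%, with a 10% chance of significance against Aerucin; 19.5% and 25.5% at r = 30%, with 14%) require that most recurrences leave Day 21 status unchanged, for instance because they fall after Day 21.

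**6. Later cures.** If a share d in each arm resolves only after Day 21, the ratio is (0.85 + d)/(0.65 + d). At the largest possible d, 0.15, it is 1.00/0.80 = 1.25. If placebo catches up more than Aerucin, it moves closer to 1.

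**7. Alternatives at equal r.**
- Resolved subjects only (0.65 × 77 = 50 and 0.85 × 77 = 65): ratio 1.00 and rejection of about 5%, but the comparison conditions on a post-randomization outcome.
- Resolved without recurrence, over all micro-ITT subjects, r = 10%: 0.65 × 0.90 = 58.5% and 0.85 × 0.90 = 76.5%. Deaths after resolution are left out of this sketch.

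**The case against.** The strongest defence is that a micro-ITT denominator preserves the randomized comparison. The 28-day probability of re-infection among all documented subjects is a legitimate absolute risk if read beside cure and mortality, which SAP 6.4.2.1 and 6.4.2.2 report on the same population. That stands, and it is why the raw rate should be kept. It does not make the p-value evidence on recurrence.

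The SAP also never writes that dead or unresolved subjects count as free of re-infection, and SAP 6.1.2 promises clearly defined denominators. This is fair: the scoring follows from the denominator, the definition and the absence of another rule. SAP 3.1 does not say that re-infection is sought only after cure, and SAP 6.4.3 relies on cultures, so the at-risk state might be culture clearance. The problem would persist if the drug raises clearance, but its size would no longer follow from 65% and 85%.

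A reader might go further and infer that the re-infection objective cannot be answered. The documents do not support that: the rate is estimable, and at r = 10% the arms differ by about 1.5 expected events. A reader might also infer that the tested rate omits the events it is named after. It does not; SAP 6.4.3 names it as the *P. aeruginosa* rate, in line with the design definition of re-infection. Only the joint label is loose.

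Finally, the proposed composite overlaps heavily with Day 28 Clinical Cure, the first secondary endpoint. That also stands, and it is a reason against deleting the raw rate.

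**Conclusion.** The concern holds as a bias in a supportive analysis. With no rule for death or non-resolution, uncured subjects and those who die uncured are favourable non-events, and the comparison tilts against a drug that raises cure. The ratio is 1.31, and at r = 10% the chance of a significant result against Aerucin is about 6% instead of 2.5%.

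The direction follows from the text. The size is illustrative: it rests on Day 21 cure standing in for ever resolved, on an assumed r that is equal in both arms, and on an unstratified version of the test. Later cures would shrink the ratio; the longer time at risk after earlier cure works the other way and is not quantified.

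Impact is limited. Re-infection is a stated objective with its own p-value, but it is absent from the endpoint lists in Protocol 7.3 and SAP 5.3, from the primary endpoint, and from the hierarchy in SAP 6.4.2. No success claim depends on it.

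**What to change.** Before database lock, amend SAP 6.4.3 as follows:

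- Make the tested comparison a micro-ITT composite in which never resolved, *P. aeruginosa* recurrence, or death by Day 28 is failure.
- Keep the raw micro-ITT re-infection rate as descriptive, and do not read a p-value on it as evidence about recurrence.
- Tabulate by arm the exclusive states: never resolved and alive; resolved without recurrence; resolved then *P. aeruginosa* recurrence; resolved then other-pathogen new infection; dead. Give the number resolved and at risk.
- Reconcile the joint label in Protocol 2.5, SAP 2.6 and SAP 6.4.3 with the separate definitions in Protocol 3.1 and SAP 3.1.

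The cost is SAP wording and one table, from statuses that sites already record. The drawback is the overlap with Day 28 Clinical Cure. The composite does not isolate recurrence either; the state table has to show where a difference arises.
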